4.0 ADVERSE AND SERIOUS ADVERSE EVENT REPORTING

The two categories of adverse reactions that will be reported to the FDA for review on form 3500A are "serious and unexpected" and "unexpected fatal or life threatening", which are assessed by the Principal Investigator as Possibly Related, Probably Related or Definitely Related to the study drug. Serious and unexpected events will be submitted to the FDA's Center for Drug Evaluation and Research (CDER) for review within 15 days of learning of the event. Unexpected fatal or life threatening events will be submitted to the FDA's Center for Drug Evaluation and Research (CDER) for review within 7 days of learning of the event.

Serious Adverse Event (SAE): An adverse event is considered serious if, in the view of the Medical Monitor, it results in any of the following outcomes:

- Death.
- A life-threatening adverse event.
- Inpatient hospitalization or prolongation of existing hospitalization (for >24 hours).
- A persistent or significant incapacity or substantial disruption of the ability to conduct normal life functions.
- A congenital anomaly/birth defect.
- Important Medical Events (IME) that may not result in death, be life threatening, or require hospitalization may be considered a serious adverse drug experience when, based upon medical judgment, they may jeopardize the subject and may require medical or surgical intervention to prevent one of the outcomes listed in this definition

Life-threatening adverse event or life-threatening suspected adverse reaction: An adverse event or suspected adverse reaction is considered "life threatening" if, in the view of either the Principal Investigator or the Medical Monitor, its occurrence places the

subject at immediate risk of death. It does not include an adverse event or suspected adverse reaction that, had it occurred in a more severe form, might have caused death.

AE Identification: The NCI Common Terminology Criteria for Adverse Events (CTCAE) provides a descriptive terminology that is to be utilized for AE reporting. The grading (severity) scale which is provided for each AE term will be used to grade the severity of the event. For this study, CTCAE version 4 will be used.

Attribution: An assessment of the relationship between the AE and the study drug. After naming and grading the event, the Medical Monitor will assign an attribution to the AE. Attributions include:

- Unrelated
- Unlikely Related
- Possibly Related
- Probably Related
- Definitely Related

Expectedness: An adverse event or suspected adverse reaction is considered "unexpected" if it is not consistent with the risk information described in the general investigational plan or elsewhere in the current protocol. For this study, the risks listed in the Myrbetriq® package insert will be used to determine expectedness (Appendix I). The Principal Investigator will be contacted as soon as possible after an event is identified at [contact] during regular business hours or paged at [contact] after regular business hours. The Principal Investigator is responsible for AE identification, documentation, grading and assignment of attribution to the study drug or the study procedures. The completed FDA 3500A form will be submitted to the following address for review:

Food and Drug Administration Center for Drug Evaluation and Research Division of Drug Oncology Products [name]

Reports will contain patient initials, age, sex, and specific information regarding the event.

All adverse events will be recorded in a study specific Adverse Event (AE) log. Written reports to the DSMC and the PN IRB will be submitted according to the PN IRB

Unanticipated Problems Involving Risks to Participants or Others (UPIRTSO) policy and only those events that meet the criteria of a UPIRTSO will be promptly reported the IRB within 10 calendar days of learning of the event.

5.0 DATA AND SAFETY MONITORING PLAN

An external data safety and monitoring committee (DSMC) will monitor the safety of study participants. The PI will report all adverse events to the DSMC that include clinically significant changes in physical exams, abnormal laboratory values and post study adverse events. Subject hospitalizations and all adverse events reported to the PN IRB will be reviewed by the DSMC. Interim analysis will be available to the DSMC after 15 participants have complete data and then again at study completion. The study biostatistician for this study will prepare the data for review by the committee and attend the DSMC meetings.

The study will be monitored according to FDA/GCP guidelines. The PI will allocate adequate time for such monitoring activities. The PI will also ensure that the Park Nicollet Institute study monitors and other compliance or quality assurance reviewers are given access to all the above noted study-related documents and study related facilities and have adequate space to conduct the monitoring. Work standards to monitor study procedures and data collection will be in accordance with Park Nicollet Institute internal investigator-initiated study audit policy and procedures.

6.0 STUDY DRUG SUPPLY

Study drug will be provided to study subjects free of charge.

6.1 Mirabegron

Mirabegron extended-release tablets will be supplied as 25 mg oval, brown, film coated tablets. Matching placebo will also be supplied.

6.1.1.1 Distribution and Shipment

Study drug (mirabegron and placebo) will be shipped to study site by Astellas Pharma US, Inc.

All study drugs and materials will be packed in appropriate storage boxes. If, upon arrival at the study site, the study drugs appear to be damaged, the sponsor will be contacted immediately.

Each shipment of study drugs for the study will contain a shipment form describing the content of shipment. This form will assist in maintaining current and accurate inventory records. When a shipment is received, the coordinator will acknowledge receipt of the study drugs by signing and dating the relevant shipping documents.

6.1.2 Known Potential Toxicities

The most frequent adverse events (0.2%) leading to discontinuation in 3 clinical trials for the 25 mg or 50 mg dose were nausea, headache, hypertension, diarrhea, constipation, dizziness and tachycardia.

Atrial fibrillation (0.2%) and prostate cancer (0.1%) were reported as serious adverse events by more than 1 patient and at a rate greater than placebo.

Table 2 lists adverse reactions, derived from all adverse events that were reported in 3 clinical trials at an incidence greater than placebo and in 1% or more of patients treated with mirabegron 25 mg or 50 mg once daily for up to 12 weeks. The most commonly reported adverse reactions (greater than 2% of Myrbetriq patients and greater than placebo) were hypertension, nasopharyngitis, urinary tract infection and headache.

Table 2 Percentages of Patients with Adverse Reactions, Derived from All Adverse Events, Exceeding Placebo Rate and Reported by 1% or More Patients Treated With mirabegron 25 mg or 50 mg Once Daily in 3 Clinical Trials

	Placebo (%)	Mirabegron 25 mg	Mirabegron 50 mg
		(%)	(%)
Number of patients	1380	432	1375
Hypertension*	7.6	11.3	7.5
Nasopharyngitis	2.5	3.5	3.9
Urinary Tract	1.8	4.2	2.9
Infection			
Headache	3.0	2.1	3.2
Constipation	1.4	1.6	1.6
Upper Respiratory	1.7	2.1	1.5
Tract Infection			
Arthralgia	1.1	1.6	1.3

Diarrhea	1.3	1.2	1.5
Tachycardia	0.6	1.6	1.2
Abdominal Pain	0.7	1.4	0.6
Fatigue	1.0	1.4	1.2

^{*}Includes reports of blood pressure above the normal range, and BP increased from baseline, occurring predominantly in subjects with baseline hypertension.

Other adverse reactions reported by less than 1% of patients treated with mirabegron in clinical trials included:

- Cardiac disorders: palpitations, blood pressure increased
- Eye Disorders: glaucoma
- Gastrointestinal disorders: dyspepsia, gastritis, abdominal distension
- Infections and Infestations: sinusitis, rhinitis
- Investigations: GGT increased, AST increased, ALT increased, LDH increased
- Renal and urinary disorders: nephrolithiasis, bladder pain
- Reproductive system and breast disorders: vulvovaginal pruritis, vaginal infection
- Skin and subcutaneous tissue disorders: urticaria, leukocytoclastic vasculitis, rash, pruritus, purpura, lip edema

Table 3 lists the rates of the most commonly reported adverse reactions, derived from all adverse events in patients treated with mirabegron 50 mg for up to 52 weeks in a fourth clinical trial. The most commonly reported adverse reactions (>3% of Myrbetriq patients) were hypertension, urinary tract infection, headache, and nasopharyngitis.

Table 3 Percentages of Patients with Adverse Reactions, Derived from all Adverse Events, Reported by Greater Than 2% of Patients Treated With Myrbetriq 50 mg Once Daily in Study 4

	Mirabegron 50 mg (%)	Active Control (%)
Number of patients	812	812
Hypertension	9.2	9.6
Urinary Tract Infection	5.9	6.4
Headache	4.1	2.5
Nasopharyngitis	3.9	3.1
Back Pain	2.8	1.6
Constipation	2.8	2.7
Dry Mouth	2.8	8.6
Dizziness	2.7	2.6
Sinusitis	2.7	1.5
Influenza	2.6	3.4
Arthralgia	2.1	2.0
Cystitis	2.1	2.3

In Study 4, in patients treated with Myrbetriq 50 mg once daily, adverse reactions leading to discontinuation reported by more than 2 patients and at a rate greater than active control included: constipation (0.9%), headache (0.6%), dizziness (0.5%), hypertension (0.5%), dry eyes (0.4%), nausea (0.4%), vision blurred (0.4%), and urinary tract infection (0.4%). Serious adverse events reported by at least 2 patients and exceeding active control included cerebrovascular accident (0.4%) and osteoarthritis (0.2%). Serum ALT/AST increased from baseline by greater than 10-fold in 2 patients (0.3%) taking Myrbetriq 50 mg, and these markers subsequently returned to baseline while both patients continued Myrbetriq.

In the fourth clinical trial, serious adverse events of neoplasm were reported by 0.1%, 1.3%, and 0.5% of patients treated with mirabegron 50 mg, mirabegron 100 mg and active control once daily, respectively. Neoplasms reported by 2 patients treated with mirabegron 100 mg included breast cancer, lung neoplasm malignant and prostate cancer.

In a separate clinical study in Japan, a single case was reported as Stevens-Johnson syndrome with increased serum ALT, AST and bilirubin in a patient taking mirabegron 100 mg as well as an herbal medication (Kyufu Gold).

6.1.2.1 Postmarketing Experience

Because these spontaneously reported events are from the worldwide postmarketing experience, from a population of uncertain size, the frequency of events and the role of mirabegron in their causation cannot be reliably determined. Urinary retention has been reported in association with mirabegron use in worldwide postmarketing experience.

6.1.3 Known Key Drug Interactions

Drug interaction studies were conducted to investigate the effect of co-administered drugs on the pharmacokinetics of mirabegron and the effect of mirabegron on the pharmacokinetics of co-administered drugs (e.g., ketoconazole, rifampin, solifenacin, tamsulosin, and oral contraceptives). No dose adjustment is recommended when these drugs are co-administered with mirabegron.

The following are drug interactions which are listed as prohibited medications:

6.1.3.1 Drugs Metabolized by CYP2D6

Since mirabegron is a moderate CYP2D6 inhibitor, the systemic exposure of drugs metabolized by CYP2D6 enzyme such as metoprolol and desipramine is increased when co-administered with mirabegron. Therefore, appropriate monitoring and dose adjustment may be necessary when Myrbetriq is co-administered with these drugs, especially with narrow therapeutic index CYP2D6 substrates, such as thioridazine, flecainide, and propafenone. Subjects on CYP2D6 inhibitors will not be allowed to participate in the study. Subjects receiving drugs which are partly metabolized via CYP2D6, but which do not require dose adjustment when co-administered with CYP2D6 inhibitors will be allowed in the study at the discretion of the PI.

6.1.3.2 Digoxin

When given in combination, mirabegron increased mean digoxin C_{max} from 1.01 to 1.3 ng/mL (29%) and AUC from 16.7 to 19.3 ng.h/mL (27%). Therefore, for patients who are initiating a combination of mirabegron and digoxin, the lowest dose for digoxin should initially be considered. Serum digoxin concentrations should be monitored and used for titration of the digoxin dose to obtain the desired clinical effect. Subjects on digoxin will be allowed in the study at the Principal Investigators discretion.

6.1.3.3 Warfarin

The mean C_{max} of S- and R-warfarin was increased by approximately 4% and AUC by approximately 9% when administered as a single dose of 25 mg after multiple doses of 100 mg mirabegron. Following a single dose administration of 25 mg warfarin, mirabegron had no effect on the warfarin pharmacodynamic endpoints such as International Normalized Ratio (INR) and prothrombin time. However, the effect of mirabegron on multiple doses of warfarin and on warfarin pharmacodynamic end points such as INR and prothrombin time has not been fully investigated. Subjects on warfarin will be allowed in the study at the Principal Investigators discretion.

6.1.4 Storage

Study drug will be stored in a secure, locked storage cabinet at room temperature (15°C to 30°C (59-86°F)). The cabinet temperature is monitored daily.

Only authorized personnel will have access to the study drugs. Study site personnel will be responsible for correct storage and handling of the study drugs. The study drugs will be dispensed by the study coordinator, under the supervision of the PI.

6.1.5 Formulation of study drug

Each Myrbetriq extended release tablet for oral administration contains 25 mg of mirabegron as the active ingredient, and the following inactive ingredients: polyethylene oxide, polyethylene glycol, hydroxypropyl cellulose, butylated hydroxytoluene, magnesium stearate, hypromellose, yellow ferric oxide, and red ferric oxide (25 mg tablet only). Matching placebo will contain the same inactive ingredients and have the same appearance as the active study drug, but will not contain mirabegron.

6.1.6 Route and administration

Each subject will take one to two tablets of Myrbetriq or matching placebo as follows: All subjects will receive one tablet of placebo daily for the first two weeks following baseline visit (visit 2). After randomization (visit 3), participants randomized to placebo will continue to receive one tablet of placebo daily until dose escalation (visit 5). At the dose escalation visit (visit 5), subjects randomized to placebo will take two placebo tablets until the end of active treatment (visit 7). Participants randomized to study drug will receive one Myrbetriq 25 mg tablet daily for two weeks, until dose escalation (visit 5). At the dose escalation visit (visit 5), subjects randomized to active treatment will have their regimen changed to 2 Myrbetriq 25 mg tablets daily until end of the active treatment phase (visit 7). Thus, all subjects will be receiving one or two identical appearing tablets daily for the entire active treatment phase. Subjects will remain blinded to treatment (placebo vs. active) for all 14 weeks of treatment.

Subjects will be instructed to take the tablets together, at the same time every morning, in one single dose. The tablets can be taken one at a time, with water, and can be taken with food or on empty stomach. Tablets should be swallowed whole and should not be chewed, cut, or crushed. To avoid confusion, subjects will be explained that although the Myrbetriq package insert instructs patients to only take one tablet a day, in this study they will be asked to take one to two tablets a day.

6.1.7 Dose schedule

Table 4 describes the daily dose schedule during each portion of the active treatment phase, by treatment assignment.

Table 4. Daily dose schedule

Treatment	From visit 1	From visit 2	From visit 3	From visit 5	From visit 7
Assignment	to visit 2	to visit 3	to visit 5	to visit 7	to visit 8
Active Drug	none	1 placebo	1 Myrbetriq	2 Myrbetriq	none
Group					

Placebo	none	1 placebo	1 placebo	2 placebo	none
Group					

6.1.8 Dose increase / Dose reduction

One scheduled dose increase will occur for the active treatment group subjects as described above at visit 5. Dose de-escalations will not be allowed prior to dose escalation (visit 5). If the subject is not tolerating study drug prior to dose escalation then the Principal Investigator will consider their withdrawal from the study. One dose de-escalation will be allowed after the dose escalation has taken place (visit 5). Thus, subjects in both treatment groups will be allowed to reduce their daily dose to 1 tablet daily, at the discretion of the Investigator. No re-escalations will be allowed due to the short duration of the study. If subjects cannot tolerate 1 tablet a day, then the Principal Investigator will consider withdrawal of the subject from the study.

6.1.9 Drug accountability

The investigator is responsible for the control of study drugs under investigation. Adequate records of the receipt and disposition of the study drug must be maintained.

Study drug accountability records should contain the following information:

- Shipment number, kit numbers, batch number, number of kits and date received for all shipments of study drug received by the site.
- Subject number, medication kit number, the date, batch number, and quantity of study drug dispensed to AND returned by the subject (when applicable).
- Kits numbers, batch number, number of kits (undispensed study drug) or number of tablets (returned study drug) for all study drug returned to the Sponsor.

6.1.10 Subject compliance

Subjects will be instructed to bring their medication kit, including used and unused bottles, with them every post baseline visit during the treatment phase for compliance and accountability checks. During each study visit (visits 3-7), the investigator and/or site coordinator will assess the subject's compliance with the prescribed regimen for the study medication. This will include checks of protocol compliance and use of study drug in order to assess the reliability of subject-generated data. Subjects who fail to comply with the study requirements may be withdrawn from the study.

Compliance with the dosing regimen will be determined by performing study drug accountability of returned study drugs used and unused. The number of used, unused and

lost tablets will be recorded in the study drug accountability records and the CRF by site personnel at every visit during the treatment phase.

A subject will be considered non-compliant if he/she misses more than 4 doses of study medication within a 28 day period (less than 85% compliance) but not on the last week prior to a visit – unacceptable noncompliance will be reported to the Medical Monitor. Examples of acceptable reasons for missing a dose are 1) if a subject develops an adverse event that the Investigator believes requires the subject's dose to be held, or 2) if a subject loses their kit of study medication and a replacement kit is requested.

6.1.11 Prior and concomitant medications

All concomitant medication that the subject is taking from the screening visit should be recorded on the concomitant medications log. In addition, any changes in concomitant medication or new medications added, including as a result of an inter-current illness must be recorded in the case report forms at each visit.

6.1.12 Prohibited medications

The following medications will not be allowed during study participation. If treatment with one of these agents is clinically necessary, then subjects will have to be withdrawn from the study:

- CYP2D6 substrates that are significantly metabolized by CYP2D6 (Atomoxetine, desipramine, dextromethorphan, metoprolol, nebivolol, perphenazine, tolterodine, venlafaxine). Medications metabolized by CYP2D6 in small proportion, such that no dosage adjustment is necessary when co-administered with CYP2D6 inhibitors will be allowed at PIs discretion.
- Antidopaminergic agents (e.g. all neuroleptics, metoclopramide).
- Anticholinergic antiparkinsonian agents (e.g. trihexyphenidyl, benztropine, orphenadrine): such agents will be allowed if a subject has been on a stable dose for 30 days prior to screening; however, such medications will not be allowed to be initiated during the study. Dose adjustment or discontinuation will be at the discretion of the Principal Investigator.
- All other antiparkinsonian agents will be allowed, if, in the opinion of the Principal Investigator they will not affect the outcome measures.
- Antimuscarinic agents used to treat overactive bladder.
- Cognitive enhancers (donepezil, rivastigmine, galantamine and memantine) will be allowed, only if the subject has been on these medications and on stable dose for 30 days prior to screening. Dose adjustment or discontinuation will be at the discretion of the Principal Investigator.

• Any other medications that, in the opinion of the Principal Investigator, may alter the outcome measures may be prohibited from the study.

If treatment with one of the prohibited medications is medically necessary during the study, then, in consideration of subject's interests, subject may be withdrawn from the study.

6.1.13 Blinding and Unblinding

Blinding will be maintained during the entire study. The investigators, study coordinators, monitors, analysis and data management will all be blinded to the subject assignment. The blind will be held by the statistician and the PI has the authority to unblind a subject.

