3.7 Randomization

After a 2-week run-in period in which all subjects take placebo in a single-blinded fashion, subjects will be randomized to a blinded dose of study drug at their randomization visit. This is a double-blind, pilot study. Neither the subject, treating physician, principal investigator, co-investigators, nor study coordinators will know to which group the subject has been randomized. The randomization scheme will be prepared by the study statistician. Study subjects will receive identical tablets in identical containers which will contain either 25 mg mirabegron extended release or placebo tablets, depending on which group they are randomized to. Study subjects will be instructed to take study drug in the morning with food and 8 ounces of water. A subject's dose assignment will be un-blinded if the Medical Monitor and PI determine it is medically necessary (for instance, allergic reaction).

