7.2 Randomization

The randomization scheme will be prepared by the study statistician per standard statistical procedures. Randomization will be a 2:1 ratio between mirabegron and placebo, and aim at equivalent sex distribution in the active treatment and placebo groups.

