7.4 Data summary

Data will be collected on case report forms for each participant at each visit and doubleentered into a secure study database. A quality check of data will occur after the first five records and prior to analysis, looking for out-of-range values and inconsistent data. The study statistician will conduct additional quality checks prior to data analyses including consistency between rounds of data entry, checking for duplicate entries, truncation of data, out-of-range values, inconsistent data and amount of missing data. Data discrepancies will be resolved and documented prior to data analysis. Missing data will not be imputed. After quality checks have been completed, a final database will be created with proper formatting and any appropriate mathematical algorithms applied including change from randomization visit (Visit 3).

Descriptive summaries will be generated for all demographic and clinical variables by study visit and treatment group including number, mean, median, standard deviation, minimum and maximum for continuous variables and number and percent for categorical variables. Summaries for change from randomization visit will also be generated. The number and screening/baseline characteristics of withdrawn participants will be recorded.

Subgroups for analyses may include treatment group, time point/study visit, age group and sex. A significance level of 0.05 will be used throughout with no adjustment for multiplicity. Normality will be tested throughout using the Shapiro-Wilk test. All analyses will be conducted on the final dataset in SAS version 9.3 or higher.

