7.4.4 Summary of safety data

Safety data and adverse events will be summarized, overall and by group, prior to each DSMB meeting and reported in the final study report.

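### Section 6.1.13 claims a blinded analysis, but the code-holding statistician also prepares DSMC data and runs the pre-analysis checks while every equivalence range except MoCA's is still open

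*Combined protocol and SAP*

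**What the plan says.** All references are to the combined protocol and SAP.

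- **Who is blinded (6.1.13):** "The investigators, study coordinators, monitors, analysis and data management will all be blinded to the subject assignment".
- **Who holds the code (6.1.13, next sentence):** "The blind will be held by the statistician and the PI has the authority to unblind a subject".
- **Who writes the allocation scheme (7.2; 3.7 agrees):** "The randomization scheme will be prepared by the study statistician per standard statistical procedures".
- **Who supplies the DSMC (5.0):** "The study biostatistician for this study will prepare the data for review by the committee and attend the DSMC meetings".
- **When (5.0):** "Interim analysis will be available to the DSMC after 15 participants have complete data and then again at study completion".
- **In what form (7.4.4):** "Safety data and adverse events will be summarized, overall and by group, prior to each DSMB meeting and reported in the final study report".
- **Who checks the data (7.4):** "The study statistician will conduct additional quality checks prior to data analyses". These cover out-of-range values, inconsistencies and the amount of missing data. The final database is built afterwards.
- **What is still open:** Section 7.4.1 fixes the MoCA range at (-2, 2). Sections 7.4.1 to 7.4.3 leave the ranges for the other equivalence measures to be taken from the literature at some time before analysis. Section 7.4 lists possible subgroups without committing to them.
- **Who may unblind (3.7):** "A subject's dose assignment will be un-blinded if the Medical Monitor and PI determine it is medically necessary". Section 6.1.13 names the PI alone and states no condition.

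**The concern.** A blinded analysis protects against choices being shaped, even unintentionally, by knowledge of who received what. Here the two sentences of 6.1.13 pull apart: analysis is blinded, yet the statistician has the code. If that person also sees results by group during the trial and then works on the data before the final database exists, the protection is absent for any choice not yet made.

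The main open choice is the equivalence margin. In a two one-sided tests analysis the margin decides the conclusion: the same confidence interval can succeed against a wide range and fail against a narrow one. A margin set after by-group data have been seen cannot be shown to be independent of them, even if a literature source is cited for it. The secondary and exploratory conclusions that mirabegron leaves non-motor and motor symptoms unchanged rest on such margins.

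**Working it through.** The plan gives no figure to reproduce on this point. The check compares role assignments and counts what is open.

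**1. Does one role do all of this?**

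| Task | Role named | Section |
|---|---|---|
| Randomization scheme | study statistician | 3.7, 7.2 |
| Holding the code | the statistician | 6.1.13 |
| Preparing DSMC data, attending meetings | study biostatistician | 5.0 |
| By-group safety summaries | not named | 7.4.4 |
| Pre-analysis quality checks | study statistician | 7.4 |
| Resolving discrepancies | not named | 7.4 |
| Setting the remaining ranges | not named | 7.4.1 to 7.4.3 |

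The titles differ slightly, but no second statistician is described. Section 3.7's own list of people kept unaware of allocation leaves the statistician out, which fits the code-holder reading and conflicts with the word analysis in 6.1.13. That the biostatistician prepares by-group data comes from joining 5.0 (who) with 7.4.4 (by group).

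**2. Would coded labels keep the summaries blind?** Section 7.1 plans 20 active and 10 placebo, a ratio of 20/10 = 2. The larger group is the active one. At the review after 15 participants, the expected split is 15 × 2/3 = 10 and 15 × 1/3 = 5. The actual split may vary, since blocking is not described. For whoever holds the list, labels conceal nothing in any case.

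**3. How many ranges are open?** Matching the instruments in 3.10 to the equivalence analyses in 7.4.1 to 7.4.3:

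- Cognition other than MoCA: Map Search, HVLT, Trail Making Test = 3.
- Secondary non-motor: PIMS, Epworth = 2. The fatigue scale would make 3; it sits under secondary procedures but is not named in 7.4.2.
- Exploratory: orthostatic blood pressure, BDI-II, BAI, constipation questions, UPDRS-6, UPDRS = 6.

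Total: 3 + 2 + 6 = 11 instruments, or 12 with fatigue. Several yield more than one score (three for HVLT, two for Trail Making), so the number of ranges is larger.

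**4. Can these ranges postdate by-group data?** Yes. The only deadline is the start of analysis, whereas DSMC data are due after 15 participants. Although 7.4.4 promises only safety summaries by group, these are informative: section 2.3 says that worsening of PD motor and non-motor symptoms is logged as an adverse event, and the exploratory measures cover such symptoms. Section 5.0 does not say what else its interim analysis contains, and 7.4.5 says there will be none. That conflict should be settled too, but the summaries in 7.4.4 stand either way.

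**The case against.** The strongest reply is that this is a wording slip in a 30-subject, single-site pilot. The double blind in 3.7 covers subjects, physicians, investigators and coordinators, and nothing here weakens it. The primary analysis is well protected: the MoCA margin, visits and two one-sided tests approach are fixed, and a normality test guides the choice between the t-test and a non-parametric alternative. Open margins affect non-primary measures only and must come from literature. A deadline is not evidence that they will be set late. A separate blinded analyst may exist without being mentioned. All of this stands, and it limits the point to the blinding statement and the non-primary measures.

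Three stronger readings are tempting, but the documents do not support them:

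- *That exclusions are decided unblinded.* Section 7.3 applies a fixed rule: participants who withdraw, or whom the PI withdraws, are left out. Sections 3.7 and 6.1.13 say the PI is blinded, and no section gives the statistician an exclusion decision.
- *That the statistician resolves discrepant values.* Section 7.4 assigns checks to that role and names nobody for resolution; 6.1.13 says data management is blinded.
- *That the bias can be sized by removing one participant with a large MoCA fall.* The documents describe no such record and no rule for removing it. The exercise would show how much one observation weighs in arms of 20 and 10, not the effect of knowing the code.

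On unblinding, 3.7 could be read as the condition and 6.1.13 as the authority. Even so, one section involves the Medical Monitor and the other does not.

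**Conclusion.** The concern holds in a limited form. As written, 6.1.13 promises a blinded analysis that the assignment of roles does not provide, and ranges for at least 11 instruments may be set after by-group data exist. The primary MoCA margin is not exposed. The documents give no basis for a numerical estimate of bias, and none is offered.

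The conclusion assumes that the statistician, the study statistician and the study biostatistician are one role, which is the natural reading but is not stated. If they are different people, the remedy for the blinding statement is to say so and describe the separation; the need to fix the ranges early remains. The unblinding clauses in 3.7 and 6.1.13 differ and must be reconciled. This review takes no view on which should prevail.

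**What to change.** 1. **Fix the open choices early.** Before the first by-group DSMC table, sign and date the equivalence range for each non-MoCA measure with its source, the test-selection rule (including which non-parametric equivalence procedure is used), the subgroups and the data-handling rules. State who resolves discrepancies.
2. **Order the work.** Merge treatment codes into the analysis dataset only after quality checks are complete and the database is locked. Produce DSMC tables from a separate extract.
3. **Correct 6.1.13.** If the code-holding statistician does the analysis, remove analysis from the blinded list. Possible text: *The study statistician prepares the randomization scheme, holds the treatment code and is not blinded. Equivalence ranges and analysis rules are signed off before any summary by treatment group is produced.* If a separate blinded analyst exists, name that role and describe the firewall instead.
4. **Reconcile 3.7 with 6.1.13** on who may unblind a subject, and 5.0 with 7.4.5 on whether an interim analysis takes place.

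Moving the code list to another custodian would not be enough, because the statistician wrote the scheme. Step 1 works even though that person cannot be blinded.

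The cost is wording and order of work, with no extra staff or data. Margins have to be settled earlier, and database lock may be slightly slower.
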